7.4.2 Concomitant Medications

Concomitant medications for the short-term double-blind treatment period will be any medication taken from start of the short-term double-blind treatment period up to the end of the short-term double-blind treatment period.

Concomitant medications for combined short-term plus long-term treatment periods will be any medication taken from the start of the short-term double-blind treatment period up to the end of the combined short- and long-term treatment periods.

Concomitant medications for both the short-term and combined short- and long-term treatment periods will be summarized using the Treated Subjects dataset by drug class and (generic) drug name. Summary tables, for allowed, as well as disallowed concomitant medications, by drug class and generic drug name will be generated.

In addition, a listing of all non-study medications taken during the study (including prior and concomitant) will be produced.

Missing and partial date handling of start and stop dates of concomitant medications is described in Section 8.7. The WHO dictionary will be used to code the non-study medication.

7.4.3 Measurements of Treatment Compliance

Percent treatment compliance will be calculated for the short-term and the combined short- and long-term treatment period for each treatment group. For each subject, percent compliance is defined as the total number of tablets taken divided by the total number of tablets that should have been taken, multiplied by 100. A subject is considered compliant if percent compliance is $\geq 80\%$ and $\leq 120\%$. The number and percent of subjects considered compliant will be summarized for each treatment group using the Treated Subjects data set.

For the short-term:

The number of tablets that should have been taken is calculated as 1 + the number of days from the first short-term double-blind treatment period dose recorded in the “Record of Study Medication” to the last short-term double-blind treatment dose, times the prescribed daily dose (i.e., 2 tablets per day, one from each bottle). The number of tablets taken is the total number of

tablets recorded (sum of bottle 1 and bottle 2) as taken based on the CRF, summed over the days counted when calculating the number of tablets that should have been taken, including the day of the last short-term double-blind treatment dose.

For the combined short- and long-term:

The number of tablets that should have been taken is calculated as 1 + the number of days from the first treatment period dose recorded in the “Record of Study Medication” to the last treatment dose, times the prescribed daily dose (i.e., 2 tablets per day, one from each bottle). The number of tablets taken is the total number of tablets recorded (sum of bottle 1 and bottle 2) as taken based on the CRF, summed over the days counted when calculating the number of tablets that should have been taken, including the day of the last treatment dose (following any adjustments for duplicate records as described in Section 7.4.1)..

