Glimepiride	1-6 mg (titrated)	IMP
Matching placebo for glimepiride	0 mg	IMP

Dapagliflozin, saxagliptin, glimepiride and their matching placebo tablets/capsules will be packaged in bottles. The tablets/capsules may contain lactose, which may cause discomfort in lactose-intolerant individuals.

Dose and treatment regimens Blinded Study Medication

Saxagliptin 5 mg tablets or matching placebo tablets, administered orally once daily, will be provided for the 156-week blinded treatment period. Saxagliptin 5 mg is the maximum recommended daily dose. No up- or down-titration of saxagliptin will be allowed.

Dapagliflozin 10 mg tablets or matching placebo tablets, administered orally once daily, will be provided for the 156-week blinded treatment period. Dapagliflozin 10 mg is the maximum recommended daily dose. No up- or down-titration of dapagliflozin will be allowed.

Glimepiride 1-6 mg or matching placebo capsules, administered orally once daily, will be provided for the 156-week blinded treatment period. During the first 12 weeks, the glimepiride/placebo dose will be slowly titrated in a stepwise blinded fashion depending on glycaemic control. For the duration of the study, FPG will be measured at the study center using a glucose analyzer provided by the Sponsor. The investigator's decision on dose titration (either upwards or downwards) will take both the plasma glucose measurements (measured prior to the visit), and the investigator's measurements at the titration visits, into account. The glimepiride/placebo dose will be titrated to optimal effect (FPG \leq 110 mg/dL [$<$ 6.1 mmol/L]) or the highest tolerable dose during the first 12 weeks. The starting dose for glimepiride/placebo is 1 mg per day (once daily), which can be further increased by increments of 1-2 mg at 3-week intervals to a maximum of 6 mg per day (maximum recommended dose as per the Summary of Product Characteristics and thus the maximum dose to be used in this study). The titration steps will be 2 mg, 3 mg, 4 mg, and 6 mg once daily if needed. In subjects for whom titration is not medically indicated at Week 3, re-assessment for titration will occur at Week 6, Week 9, and Week 12.

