If a subject is committed to participation, completes the lead-in period, and continues to meet eligibility criteria at the randomization visit, he or she will be randomized and will receive either saxagliptin 5 mg, co-administered with dapagliflozin 10 mg, plus metformin, or glimepiride plus metformin in a double-blind fashion. Subjects will continue to receive background metformin ≥ 1500 mg/day throughout the duration of the study, unless metformin treatment is temporarily withheld due to decreased creatinine clearance (CrCl; [Section 3.5](#)).

Subjects will return to the site every 3 weeks to enable titration of glimepiride from Week 3 up to Week 12, and then approximately every 12 to 13 weeks until the last visit (up to Week 156) for assessment of events related to the objectives of the study, tolerability and safety. Assessment of treatment compliance and provision of IMP will be done at these visits.

Dose and Treatment Regimens Blinded Study Medication

Saxagliptin 5 mg tablets or matching placebo tablets, administered orally once daily, will be provided for the 156-week blinded treatment period. Saxagliptin 5 mg is the maximum recommended daily dose. No up- or down-titration of saxagliptin will be allowed.

Dapagliflozin 10 mg tablets or matching placebo tablets, administered orally once daily, will be provided for the 156-week blinded treatment period. Dapagliflozin 10 mg is the maximum recommended daily dose. No up- or down-titration of dapagliflozin will be allowed.

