2 STUDY DESCRIPTION

2.1 Study Design

The CV181-365 study is an international multicenter, randomized, double-blind, active-controlled, parallel-group Phase 3b study. The primary endpoint is the change from baseline in HbA1c with saxagliptin in combination with dapagliflozin on top of background therapy with metformin, compared to glimepiride. The primary endpoint of HbA1c will be assessed at 52 weeks, however, the trial will continue with a 104-week blinded extension. Subjects with documented T2DM treated with a stable dose of metformin will be enrolled. All subjects should be treated according to regional standards of care for diabetes. Subjects must be receiving metformin in accordance with the product label for their country. Approximately 440 subjects meeting all eligibility criteria will be randomized (1:1) to receive either saxagliptin co-administered with dapagliflozin or glimepiride. Enrollment of subjects based on disease state, and geographic region will be monitored and may be capped to ensure adequate representation. All potentially eligible subjects will undergo a screening visit. Each subject will sign an Informed Consent Form (ICF) prior to having any screening evaluations performed. Subjects who fulfill all eligibility requirements will enter a 2-week screening period and a 2-week lead-in period, during which they will continue their background medication with at least 1500 mg metformin. Approximately 2 weeks after entering the lead-in period, subjects will be expected to undergo a randomization visit. Subjects may withdraw prior to the randomization visit, or be withdrawn by study staff for any reason. At this visit, subjects will be re-evaluated by study staff to determine if after testing performed at the screening visit, after assessment of compliance, and any clinical changes that may have occurred during the lead-in period, the subject remains eligible and committed to participation in the study. If for any reason, prior to or during the randomization visit the subject is no longer eligible or interested in participating in the trial, he or she will be considered a lead-in failure, will not be randomized, and will not have additional follow up. If a subject is committed to participation, completes the lead-in period, and continues to meet eligibility criteria at the randomization visit, he or she will be randomized and will receive either saxagliptin 5 mg co-administered with dapagliflozin 10 mg plus metformin and matching placebo or glipimeride plus metformin and matching placebo in a double-blind fashion. Subjects will return to the site every 3 weeks to enable

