
titration of glimepiride from Week 3 up to Week 12, and then approximately every 12 to 13 weeks until the last visit (up to Week 156) for assessment of events related to the objectives of the study, tolerability and safety. Assessment of treatment compliance and provision of investigational product (IP) will be done at these visits.

Saxagliptin 5 mg tablets or matching placebo tablets will be provided, administered orally once daily for the 52-week double-blind treatment period and the 104-week subject and site blinded extension period. Saxagliptin 5 mg is the maximum recommend daily dose. No up- or down-titration of saxagliptin will be allowed. Dapagliflozin 10 mg tablets (also the maximum recommended daily dose) or matching placebo tablets will be provided, administered orally once daily for the 52-week double-blind treatment period and the 104-week subject and site blinded extension period. No up- or down-titration of dapagliflozin will be allowed.

[figure not shown]
Glimepiride 1-6 mg or matching placebo capsules, administered orally once daily, will be provided for the 156-week blinded treatment period. During the first 12 weeks, the glimepiride dose will be slowly titrated in a stepwise blinded fashion depending on glycemic control. For the duration of the study, FPG will be measured at the study center using a glucose analyzer provided by BMS. The investigator's decision on dose titration (either upwards if no issues with hypoglycemia or downwards if recurrent hypoglycemia occurs) will take both the plasma glucose measurements (measured prior to the visit), and the investigator's measurements at the titration visits, into account. The glimepiride dose will be titrated to optimal effect ($FPG \leq 110$ mg/dL [≤ 6.1 mmol/L]) or the highest tolerable dose during the first 12 weeks. The starting dose for glimepiride is 1 mg per day (once daily), which can be further increased by increments of 1-2 mg at 3-week intervals to a maximum of 6 mg per day (maximum recommended dose in the Summary of Product Characteristics and thus the maximum dose to be used in this study). The titration steps will be 2 mg, 3 mg, 4 mg, and 6 mg once daily if needed. In subjects for whom titration is not medically indicated at Week 3, re-assessment for titration will occur at Week 6, Week 9, and Week 12.

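### SAP 7.4.3 scores compliance on two units a day from two unnamed bottles, but each subject is assigned three once-daily products, so subjects can be misclassified when intake differs by product

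*SAP*

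**What the plan says.** SAP 7.4.3 defines percent compliance as units taken over units that should have been taken, and calls a subject compliant from 80% to 120% inclusive. For the short-term and the combined period alike, the denominator is the inclusive number of days from first to last dose, "times the prescribed daily dose (i.e., 2 tablets per day, one from each bottle". The numerator is the "sum of bottle 1 and bottle 2) as taken based on the CRF". Neither bottle is linked to a product. SAP 8.10, the other place where the calculation might be defined, only refers back to 7.4.3.

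The regimen has three products:

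- Protocol 3.1: "Saxagliptin 5 mg tablets or matching placebo tablets, administered orally once daily, will be provided for the 156-week blinded treatment period".
- Protocol 3.1: "Dapagliflozin 10 mg tablets or matching placebo tablets, administered orally once daily, will be provided for the 156-week blinded treatment period".
- SAP 2.1: "Glimepiride 1-6 mg or matching placebo capsules, administered orally once daily, will be provided for the 156-week blinded treatment period". On dose levels above the 1 mg start: "The titration steps will be 2 mg, 3 mg, 4 mg, and 6 mg once daily if needed".

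On packaging, the Protocol Synopsis says: "Dapagliflozin, saxagliptin, glimepiride and their matching placebo tablets/capsules will be packaged in bottles". SAP 2.1 describes the arms as saxagliptin and dapagliflozin "plus metformin and matching placebo or glipimeride plus metformin and matching placebo in a double-blind fashion". SAP 7.4.1 also names three study treatments when it deals with duplicate exposure records.

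**The concern.** A rule of two units a day cannot cover three products that are each taken once a day, so some of the assigned study drug falls outside the compliance measure. As the bottles are not named, a reader cannot tell which product that is. On some readings, one arm is scored without any of its active drug.

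The compliance summaries for both periods rest on this formula. Relevant protocol deviation (RPD) 10 in SAP Table 7.2-1 applies the same 80% and 120% limits to overall compliance and excludes a failing subject completely from the Evaluable Subjects data set. A scoring error could therefore also reach the deviation counts and the Week 52 Evaluable-set analysis.

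**Working it through.** **Inputs.** Two units a day from two bottles (SAP 7.4.3). Three once-daily products (Protocol 3.1, SAP 2.1). Glimepiride capsules of 1, 2 and 4 mg (Protocol 4.1). Dose levels of 1, 2, 3, 4 and 6 mg (Protocol 4.1, SAP 2.1). Limits of 80% and 120% (SAP 7.4.3 and Table 7.2-1).

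**Can the plan's figure of 2 be reproduced?** Only by leaving something out:

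| Reading of the two bottles | Not counted | Consequence by arm |
|---|---|---|
| Saxagliptin and dapagliflozin tablets | Capsules | Glimepiride arm scored on placebo only |
| Two capsule bottles | Both tablets | Combination arm scored on placebo only |
| One tablet, one capsule bottle | The other tablet | Combination arm scored on one of its two active drugs |
| Active products only | All placebo | Gives 2 in the combination arm, but only one product in the glimepiride arm |

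Metformin cannot be one of the bottles, because the sponsor does not supply it (Protocol 4.2).

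**Units assigned per day.** 1 + 1 + k, where k is the number of capsules. If doses are made up from the listed strengths, k is at least 1 at 1, 2 and 4 mg, giving at least 3 units. At 3 mg (1 + 2) and 6 mg (2 + 4), k is at least 2, giving at least 4.

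**Units left out.**
- Short-term, 52 × 7 = 364 days: 2 × 364 = 728 expected under the formula, against at least 3 × 364 = 1,092 assigned.
- Combined, 156 × 7 = 1,092 days: 2 × 1,092 = 2,184 against at least 3 × 1,092 = 3,276.

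This measures coverage. It is not the error in the percentage, as the next step shows.

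**Equal intake.** If every product is taken to the same extent a, the formula gives 2a/2 = a and the full count gives 3a/3 = a. The score is correct.

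**Unequal intake.** Take one unit a day per product, two products fully taken and the third taken to extent x. Overall compliance is (2 + x)/3, which equals 80% at x = 0.40.

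- Third product uncounted: the formula gives (1 + 1)/2 = 100% whatever x is. For x below 0.40, overall compliance is below 80%; at x = 0 it is 2/3 = 66.7%.
- Third product counted: the formula gives (1 + x)/2, which reaches 80% only at x = 0.60. At x = 0.40 it gives 70% against 2.4/3 = 80% overall. Just below x = 0.60 it gives just under 80% against about 2.6/3 = 86.7%. These subjects are scored non-compliant although overall they are compliant.
- Two capsules a day, capsules uncounted: overall compliance is (2 + 2x)/4. At x = 0.50 it is 75%, while the formula gives 100%.

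**Half a correction.** Adding the third product to the numerator alone gives 3/2 = 150% for a fully adherent subject, above the 120% limit.

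**Route to the efficacy analyses.** RPD 10 does not cite 7.4.3, but 7.4.3 is the only compliance formula in the SAP. SAP 7.5.1 (like Protocol 8.2 and 8.4.2) runs the Evaluable-set analysis only if more than 10% of subjects in a treatment group have relevant deviations. SAP 7.5.2 lists that analysis without the condition. SAP 6.3.5 confines the Evaluable set to Week 52, but deviations are still summarised for the combined period.

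**The case against.** The strongest reply is that numerator and denominator are restricted to the same two bottles, so the ratio is consistent within itself. This stands. A reader might infer from 728 against 1,092 units that reported compliance is wrong by a third. The documents do not support that, because equal intake gives the same percentage. Every misclassification above needs markedly different intake between products, and no intake data by product are given.

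Other safeguards exist. RPD 8 and RPD 9 cover two or more consecutive weeks without study medication, or with incorrect medication or dosing, and are not limited to two bottles. Protocol 4.7 has sites assess compliance by interview and a count of returned tablets. These reduce the practical risk but do not correct the 7.4.3 score.

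The word tablets might be meant to leave out capsules. That is unlikely: SAP 7.4.1 and 8.6 use tablet counts to define interruptions and the first and last dose of study medication in general. If it were meant, the glimepiride arm would be scored on placebo alone.

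The unit count is also partly inferred. The term double-dummy does not appear. That every subject takes all three products follows from matching placebo in both arms, the titrated glimepiride/placebo dose (Protocol Synopsis) and the different appearance of the three products (Protocol Table 4-1). The Amendment 05 log records the removal of a table on a two-bottle glimepiride kit. This is superseded text and not an error, but it shows that capsules per dose and bottle identity cannot be settled from the strengths alone. At least 3 units a day holds in any case.

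**Conclusion.** The formula as written omits at least one assigned product and is inconsistent with SAP 2.1, SAP 7.4.1 and Protocol 3.1. The compliance summaries for both periods can be wrong, in either direction, when intake differs by product. How many subjects this concerns cannot be estimated. The numerical thresholds assume one unit a day counted from each of two dispensed product bottles, and one capsule a day unless stated otherwise.

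Two further inferences go too far. One is that a particular arm is in fact scored on placebo: this depends on which bottles are meant, and the SAP does not say. The other is that the Week 52 per-protocol result is compromised: this requires that RPD 10 uses the formula, that the analysis is run (more than 10% with relevant deviations, if the SAP 7.5.1 condition governs) and that some subjects change status. The primary analysis uses the Randomized Subjects data set and is unaffected. The point is worth correcting because the rule is prespecified, ambiguous and cheap to repair.

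**What to change.** In SAP 7.4.3, for both periods, name the bottles and count all three products in both numerator and denominator, using the number of units assigned at each glimepiride/placebo dose level. Keep the 80% to 120% rule on the overall score. State in Table 7.2-1 that RPD 10 uses this result. No dose or clinical rule changes.

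SAP version 3 was written while the short-term report was being prepared, and SAP 2.3.1 provides for unblinding the short-term database for reporting. The correction can therefore be prospective only for the combined-period compliance and deviation summaries. Any Week 52 recalculation of compliance or of the Evaluable set should be labelled post hoc.

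Reporting compliance by product is optional. It would show what a pooled score can hide: 40% intake of one product still gives (2 + 0.4)/3 = 80%.

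The cost is SAP wording and a little more programming. The data appear to be available: doses taken pass from the diary to the eCRF (Protocol 5.2), amounts dispensed and returned are recorded at each visit (Protocol 4.7), and SAP 7.4.1 already handles exposure records by product. The downside is that some subjects may change compliance status in either direction, and a Week 52 recalculation may differ from figures already reported.

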7.5 Efficacy

7.5.1 Overall Efficacy Summary

All efficacy analyses will be performed using the Randomized Subjects data set. In addition, at the ST analysis, the primary efficacy analysis will be performed using the Evaluable Subjects data set if > 10% of subjects in any treatment group have relevant protocol deviations.

Unless otherwise specified, all analyses will be done using values prior to rescue/intensification of treatment or treatment discontinuation (plus a tolerance window after last dose as detailed in Section 0). For the endpoint of the proportion of subjects achieving a therapeutic glycemic response at Week 52/Week 156, all available data will be used, but subjects rescued prior to Week 52/Week 156 will be treated as non-responders.

The comparator (glimepiride plus metformin) will be tested against saxagliptin, in co-administration with dapagliflozin plus metformin, for the primary efficacy endpoint at the alpha = 0.05 level (two-sided). The secondary efficacy endpoints will then be tested sequentially, each comparison tested at the alpha = 0.05 level (two-sided). The following testing hierarchy (shown in order of the step-wise testing sequence) for treatment comparisons will be used:

- Mean change from baseline in HbA1c at Week 52 (primary endpoint).
- Mean change from baseline in total body weight at Week 52.
- Percent of subjects achieving a therapeutic glycemic response, defined as HbA1c < 7.0%, at Week 52.
- Mean change from baseline in systolic blood pressure (SBP) at Week 52.
- Time to treatment intensification (addition of insulin or other glucose-lowering agent for rescue therapy or discontinuation for lack of glycemic control) during the 52-week double-blind treatment period.

If all the above five comparisons performed for the short-term analysis are statistically significant, the following two comparisons will be tested sequentially for the short-term plus long-term analysis:

- Time to treatment intensification (addition of insulin or other glucose-lowering agent for rescue therapy or discontinuation for lack of glycemic control) during the 156-week treatment period.
- Proportion of subjects achieving a therapeutic glycemic response, defined as HbA1c < 7.0%, at Week 156

Analyses of exploratory endpoints specifically designed for sub-studies (CGM and MRI-PDFF) will be performed using the subsets of the Randomized Subjects data set for the sub-studies.

7.5.2 Primary Efficacy Analysis

The primary endpoint is the change in HbA1 from baseline at Week 52 visit. The primary analysis of the change in HbA1c from baseline at Week 52 visit will be based on a longitudinal repeated measures analysis using “direct likelihood”. The model will use subjects in the primary efficacy data set (i.e., randomized subjects data set) who have a baseline assessment and at least one post-baseline double-blind treatment period assessment. The SAS procedure PROC MIXED will be used. The preferred model will include the fixed categorical effects of treatment, week, and treatment-by-week interaction as well as the continuous fixed covariates of baseline measurement and baseline measurement-by-week interaction (see Model 7.1.2.1 in Section 7.1.2). An unstructured matrix for the within-subject error variance-covariance will be used. The denominator degrees of freedom will be calculated according to the Kenward-Roger method. A number of back-up models are defined in Section 7.1.2 in case of non-convergence of the preferred model or other issues. Data collected after the initiation of rescue medication will be excluded. Data collected outside the analysis window (defined in Section 8 of this SAP) after subjects discontinued double-blind study medication will also be excluded from the primary analysis. Point estimates and 95% confidence intervals for the mean change within each treatment group as well as the difference in mean change between the saxagliptin plus dapagliflozin versus glimepiride will be calculated.

Sensitivity Analyses

The following sensitivity analyses will be carried out for the primary end point for the ST data/at week 52:

- Primary analysis will be repeated using Evaluable Subjects data set.
- Primary analysis will be repeated using all available values regardless of rescue or treatment discontinuation
- An ANCOVA analysis using values prior to rescue or treatment discontinuation (LOCF will be used if the week 52 value is not available)
- Analyses to address missing values (described below in Section 7.5.4)
 - Analysis using multiple imputation return-to-baseline
 - Tipping point analysis

The following sensitivity analyses will be carried out for the ST+LT data/at Week 156 are: .

- Change from baseline in HbA1c at week 156, ANCOVA (LOCF) using the Randomized subject data set - completers not requiring glycemic rescue therapy, (defined as subjects who

took at least one dose of randomized study medication, completed the LT phase, and did not take any glycemic rescue therapy during the ST or LT treatment period)

- Change from baseline in HbA1c at week 156, regardless of rescue and treatment discontinuation, repeated measures analysis using the Randomized subject data set

